The upper extremity is completely attached by the axial skeleton, especially through the clavicle and the acromioclavicular articulation (AC)(1). The previously mentioned articulation is a diarthrodial joint. The stability of this articulation is caused by coracoclavicular ligaments in the vertical plane and the acromioclavicular ligaments in the horizontal plane(2). The AC luxation is a common pathology in youth and athletes who participate in contact sports which has a 9,2 per 1000 incidence between inhabitants every year represented between 30% to 50% from shoulder injuries in young athlete, it is most common in men than women with a ratio of 8:1(3). It's main injury mechanism is direct trauma while the shoulder is adducted and less frequently is the indirect mechanism of dropping the arm in an extended motion(4). In the year 1963, Tossy et al(5) for the first time described and classified some of the patterns of luxation AC, which was then extended to 6 AC luxation degrees and published by Rockwood in the year 1984 becoming the first most accepted and used till this day(6). There have many techniques of conservative treatment and surgery management as a treatment for all time of laxation AC (Rockwood grades I-VI) written as time passed by, although literature suggests and supports the conservative treatment for grades I and II and the surgical management for grades IV-V-VI, the optimal treatment for grade III injuries is still controversial(7). In regards to these type of injuries, taking into account the importance of medial stability an agreement was taken by the committee of the upper extremity of the International Society of Arthroscopy, Knee Surgery and Orthopedic Sports Medicine (ISAKOS), which suggests that a subdivision of the III grade of Rockwood in IIIA when the AC articulation is stable and the IIIB when the AC articulation is unstable(8), helping to differentiate and identify the patients with grade III Rockwood in a better manner who will be benefited from a surgical treatment.

To evaluate the correct AC luxation ligaments, the radiological evaluation must include a projection of bilateral, axillary Zanca and Alexander (also known as Basmania). This last projection has increased its relevance in the past couple of years since it can help us to differentiate whether there's a presence or an absence of medial instability in the case of Rockwood III AC luxation(9). Till this day there are no actual standardized measurements that guide the correct manner of treating it with a good variability, Zumstein et al(10) proposed 2 new quantitative parameters to evaluate the vertical and horizontal instability

and based on the Alexander view. To evaluate the vertical stability the use of the vertical distance between the center of the acromion and the midpoint of the lateral clavicle (AC-DC) and to evaluate the horizontal stability he used the distance of the center of the glenoid and lateral clavicle (GC-PC). Both parameters were shown to be trusted sources with excellent validity, which helped guide the treatment for some AC luxation, especially for Rockwood grade II and III injuries.

Despite the numerous described surgical techniques, currently more than 160, do not show evidence of superiority of one in specific and there is no agreement whether it is necessary to stabilize only the AC articulation in the vertical, horizontal or both planes(11). In this case more attention is focused on the complex AC ligament standing out the superior AC band as its main horizontal stabilizer(12), which does have an injury and in the process of insufficiently healing and repairing it can contribute up to 50% of horizontal instability in the AC articulation(13). Many studies demonstrate that the horizontal instability can have an important clinical relevance associated with the worst functional postsurgical results(14–16) which during the past couple of years has increased the interest of conducting many surgical techniques to better the horizontal stability and so the functional results after surgery(17). Although there have been many advances in surgical techniques during the time, the percentage of complications are still considerable, with up to 14% of inoperable complications, 21% reduction loss and 10% remains in revision surgery(4). With the result of minimizing complications and obtaining better functional results arises the idea of conducting the randomized clinical trial.

INVESTIGATION QUESTIONING

“In patients with an acute and unstable acromioclavicular luxation, the coracoclavicular fixation with stabilized acromioclavicular has a clinical impact to decrease of complications and better its functionality?”

OBJECTIVES

General objectives

- To observe the clinical impact of the fixed coracoclavicular with acromioclavicular stabilization and compare it with the isolated coracoclavicular stabilization in the management of the unstable acromioclavicular luxation.

Specific objectives

- Evaluate the functionality levels and postoperative pain of the surgically managed acromioclavicular luxation.
- Evaluate the variation of the post-operative radiological parameters (coracoclavicular distance) in the surgical management of the luxation of acromioclavicular ligaments.

- Evaluate the incidence of postoperative complications in surgical management of luxated acromioclavicular joints.

METHOD

The unstable acromioclavicular luxation evaluated and diagnosed patients will be admitted by on duty Traumatologists at the urgency services of Hospital [name] Aravena de Temuco. The unstable acromioclavicular luxation that are surgically managed according to the instability criteria found in international literature (Rockwood IIIb, IV, V and VI).

The length of the study will be of at least 1 year with the option of continuing it for 2 years. The coracoclavicular fixation with and without acromioclavicular stabilization will be compared making up two investigation groups.

The patients that fulfill the requirements and criteria for inclusion will be invited to form part of the study where they will need to evaluate and sign an informed consent form.

It will be randomized by block using a computer system. The documents will be printed and into sealed envelopes. Before the surgery one of the envelopes will be chosen, this envelope will contain one of the 2 techniques from which the surgeon will use in the procedure. Postoperative evaluations will be done, the patients will be controlled by a surgeon from a different team, which will not know the surgical protocol. The first control will be done at 3 weeks postoperative, then on the 3, 6, 12, and 24 months. During the controls the clinical functionality will be evaluated with 3 scores (ASES, Nottingham and Constant) and the eventual clinical or radiological complications using an x-ray with Bilateral Zanca view. Lastly, the need of analgesia will be consulted, and the presence of complications will be evaluated.

Statistically there will be 0.05 alpha used and there will be protocol analysis, as well as, by intent to treat for calculation of RR, RRR, RAR, NNT, NNH. Finally, there will be analysis done by subgroups of ages 15-40 and 40-65 years, sex, and acromioclavicular luxation grade according to Rockwood, affected side and preoperative evolution time. Lastly, the need of analgesia will be consulted, and the presence of complications will be evaluated.

ELECTION OF DESIGN

Our question is about therapy, from which is the best kind that will give us an estimate to the truth is through a randomized clinical trial so that we decrease biases. The 2 surgical techniques are currently valid alternatives, and they are done in the Hospital [name] Aravena on a routinary basis, so there are no ethical dilemmas in regard to added adverse events.

INCLUSION CRITERIA

- Rockwood IIIB, V, and VI acromioclavicular luxation
- Less than 14 días of progression time since the lesion
- Patient over the age of 15
- Possibility of clinical monitoring
- Informed and validated consent by the ethics committee

EXCLUSION CRITERIA

- Surgery previously done on the clavicle and/or ipsilateral acromioclavicular, contralateral and/or bilateral articulation.
- Neuropathy of motor or mixed upper extremities.
- Exposure of an acromioclavicular injury.
- Fractures associated with clavicles, scapula and/or ipsilateral humerus.
- Function alterations concerning the previously mentioned extremity.
- Functional alterations of the contralateral extremity.
- Disease that can evolve with neuropathy during the study period (Multiple Sclerosis, Vasculitis, badly controlled Diabetes with progressed damage, etc.)

PRIMARY OUTCOME

- The clinical impact of the daily strength, proprioception, range of movement and decrease of pain (functional Score)
- Complication rates (fail of the implant, loss of the reduction, clavicular or coracoid fracture, pain associated with the implant, infections, etc.)

SECONDARY OUTCOME

- Evolution of adduction force according to the postoperative period.
- Evolution of mobility rate according to the postoperative period.
- Results of the radiological variable according to the postoperative evolution time.
- Need of postoperative analgesic.
- Revision surgery rate according to the postoperative evolution.
- Presence of side effects.

SURGICAL TECHNIQUE

The procedure will be done with combined anesthesia, using general and locoregional anesthesia with an interscalene block. The patient will be placed in supine position on top of an orthopedic bed and an interscapular cushion. Using the gel pads, all of the bone

prominences are protected. The head needs to be reassured that it is in a secure and correct position. The arm that will not be intervened must remain in a neutral position while the other is prepared to be sterile manner and positioned along with the adducted body. Finally, it is covered with standard sterile drapes.

Once the patient is in the correct position, the relevant bone prominences of the shoulder are palpated and identified (clavicle, acromion, and the coracoid process) and the initial incision is marked using a surgical pen, starting on the Langer lines to create a more aesthetic scar. With a number 15 scalpel we create an incision in the bretel “continue the line of the strap of the brassiere” and we continue to dissect the subcutaneous tissue in the same direction until exposing the deltotrapezial fascia, which is opened using Metzenbaum scissors parallel to the clavicle, achieving a flap that when it's raised towards the inside we are able to see the upper and lower clavicle and coracoid process. As we palpitate we can identify the subcoracoid space and using a subcoracoid suture passer we pass a guiding suture maintaining it with mosquito forceps. With a surgical ruler over the top face of the clavicle we mark a 1 cm of the most lateral part of the clavicle to do the first tunnel with a 2,5mm drill from the top to the bottom, then we stabilize a 3-hole third plate with 3 holes and a screw in the previously done hole. Continuing with the subcoracoid of 1 Fiberwire double number 2 and a thread of Fibertape using a guide suture. Both of the remaining holes of the 3-hole third plate are drilled in the direction of the coracoclavicular ligaments so that the double Fiberwire and the thread of Fibertape with Nitinol can pass through in a retrograde manner. Using the Fiberwire we do a knot over the 3-hole third plate, then using fluoroscopy we visualize the adequate coracoclavicular reduction continuing to tie the Fibertape with a knot. It's important not to cut the remaining suture so that it is set aside for the next step. Guided by fluoroscopy, we made an 8mm incision in the lateral edge of the acromion, to perform an anterior and posterior clavicular tunnel using an anterior cruciate ligament guidewire. Using the first tunnel that goes through the Polyglactin stitch, fetching back the thread from the previous one, we go back in the same retrograde manner using the Fiberwire threads and the Fibertape that were previously mentioned. Finally, both the remaining Fiberwire and Fibertape are tied using a surgical knot achieving AC fixation.

POSTOPERATION

After the surgical stabilization on the AC articulation, we indicate that the immobilization of the shoulder with a sling for 2 weeks, which is the moment where the patients will be able to begin to move passively under shoulder level with the assistance by physical therapist. Strengthening is allowed once the patient can fully complete the movement, which is generally around the 6th to 8th week. Generally, we allow the patient to retake sports 4 to 6 months after surgery.

RISK OF ADVERSE EVENTS

There are no additional adverse risks in any surgery of this kind. As mentioned previously, the 2 accepted techniques are accepted and utilized by our service currently, therefore,

there will be no action that will increase the risk of the surgery in comparison to a common surgical procedure.

There are no studies that show variations in regard to the pain response of the treatment between the two procedures, but there should not be any differences in that aspect. Either way, every case will be monitored regarding the response of the analgesia, and it will be adjusted according to the patients' necessities.

The irradiation from the x-ray taken of the extremities is equivalent to 0.001 mSv of effective radiation (19). Since the x-ray control used in this procedure will be normal, there will only be 4 x-rays taken, without exceptions, which results in an insignificant additional increase in the risk of patient developing cancer due to the test.

In any case, the complications will be detected in an early manner during the evaluations done by the investigation team, where these will be handled and monitored, and additional controls will be done if necessary.

CONSENT PROCESS

The responsible investigator and their collaborators are in charge of receiving the consent form given by the patient. This will be solicited in a private premises where the patient and their family members will be informed about the nature of the investigation, taking the necessary time to answer all questions.

The patient will be able to take the document of consent and after its signature, later a copy of the document will be provided. If the patient needs to further analyze the document with more detail or in case that they do not want to participate they are free to take a copy to inspect and analyze.

The patient may withdraw from the study whenever they wish.

RESPONSIBLE OF RECEPTION OF CONSENT FORM

(Hospital Hernán Henríquez Aravena)

- [name] [name]
- [name] [name]

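### The protocol generates a block sequence but assigns by an envelope that is chosen; it should say that the next numbered envelope is used and tied to the patient before it is opened

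*Protocol*

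**What the plan says.** Allocation is described only in the METHOD section of the protocol, in three consecutive sentences.

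- Generation: "It will be randomized by block using a computer system".
- Concealment: "The documents will be printed and into sealed envelopes".
- Assignment: "Before the surgery one of the envelopes will be chosen, this envelope will contain one of the 2 techniques".

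There are two arms: "The coracoclavicular fixation with and without acromioclavicular stabilization will be compared making up two investigation groups". Consent is described before the envelope step. Follow-up is separated from the operating team: "the patients will be controlled by a surgeon from a different team, which will not know the surgical protocol". The closing paragraph of METHOD plans a per-protocol analysis "as well as, by intent to treat for calculation of RR, RRR, RAR, NNT, NNH". Under ELECTION OF DESIGN the protocol explains that the question is best answered "through a randomized clinical trial so that we decrease biases", and says that both techniques are already routine at the hospital.

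The protocol gives no sample size, block size, allocation ratio or number of envelopes.

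**The concern.** A block list is an ordered sequence. It keeps the arms close in size only if patients receive the entries in that order. A step in which somebody picks an envelope does not, on its wording, carry out the sequence just generated.

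The second part concerns the record. Nothing in the described step ties an envelope to a patient before it is opened. The operating surgeon necessarily learns the technique at opening and can perform either one. If an envelope were opened and replaced by another, the protocol describes nothing that would show it. Intention to treat needs the first assignment. If the replacement envelope were taken for that assignment, the risk ratio and the measures derived from it would compare patients by final envelope under an intention-to-treat label. The different-team surgeon protects outcome assessment, not allocation.

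A statistical analysis plan cannot repair this afterwards, because it cannot restore an assignment that was not recorded at the time.

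**Working it through.** The protocol has no figure on this point to reproduce. The check is a comparison of the text, followed by two illustrations of scale. Every input marked *assumed* is not in the document.

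**1. The text.** Generation is by block, so order matters. Concealment is by sealed envelope, with no numbering mentioned. Assignment is by choosing. No other section adds a next-in-sequence rule, a patient identifier on the envelope, or an opening record. The document neither describes these nor rules them out.

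**2. Balance under a blind pick.** *Assumed:* 1:1 allocation; 40, 60 or 100 envelopes; a blind pick from the whole stack; block size 4 or 6.

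- Opened in list order, the running difference between arms never exceeds half the block: 2 for blocks of 4, 3 for blocks of 6.
- With a blind pick, the number x in one arm after n = N/2 of N envelopes is hypergeometric: P(x) = C(N/2, x) · C(N/2, n − x) / C(N, n).
- For N = 40 and n = 20, a difference of at most 2 means x = 9, 10 or 11: 0.205 + 0.248 + 0.205 = 0.657 before rounding of the terms. So P(difference > 2) = 0.343. For N = 60 it is 0.439, and for N = 100 it is 0.549.

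This is lost balance, not bias. It disappears if every envelope is used, and it does not arise if the pick is made only among the current block's envelopes.

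**3. Scale of a selective exchange.** Input from the document: 0.21, from the introduction's literature figures ("21% reduction loss and 10% remains in revision surgery"), used here as the overall risk. *Assumed:* no true difference between techniques; half of patients at k times the risk of the rest; a share s of the higher-risk patients who first drew technique B is exchanged to A; no exchange in the other direction.

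- Risks: k = 2 gives 0.28 and 0.14; k = 3 gives 0.315 and 0.105. Each pair averages 0.21.
- Higher-risk share of all patients: in A, 0.5(0.5 + 0.5s); in B, 0.5(0.5 − 0.5s). Lower-risk share: 0.25 in each.
- Exchanged share of all patients: 0.25s, which is 2.5% at s = 0.1 and 7.5% at s = 0.3.
- k = 2, s = 0.1: A = (0.275 × 0.28 + 0.25 × 0.14)/0.525 = 0.2133; B = (0.225 × 0.28 + 0.25 × 0.14)/0.475 = 0.2063; RR = 1.034.
- k = 3, s = 0.3: A = (0.325 × 0.315 + 0.25 × 0.105)/0.575 = 0.2237; B = (0.175 × 0.315 + 0.25 × 0.105)/0.425 = 0.1915; RR = 1.168.

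| | s = 0.1 | s = 0.2 | s = 0.3 |
|---|---|---|---|
| k = 2 | 1.034 | 1.070 | 1.109 |
| k = 3 | 1.051 | 1.107 | 1.168 |

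If exchanges are unrelated to risk, or if the first draw is recorded and analysed, RR = 1.000.

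**The case against.** The case against is substantial.

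- **Translation.** The point about order rests on one verb in a roughly translated text. It may only mean that an envelope is taken. This stands, and is why the point is limited to a literal reading.
- **A blind pick is random.** This stands. Departing from list order costs balance at most.
- **Traceability is a separate matter.** The lack of a record would be the same if the sentence said that the next envelope is taken. That is true. The two belong together only because one replacement sentence settles both.
- **An exchange would breach the protocol.** One envelope is chosen and its technique used; no second draw is provided for. Consent comes first, the envelopes are sealed, and both techniques are accepted locally. This stands too: nothing suggests that exchanges occur or are expected.
- **The risk-ratio range is hypothetical.** Both k and s are assumed, all exchanges run one way, and the 21% is a literature figure for a single complication. The range is a scale, not an estimate for this trial.

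A reader might also infer that an exchanged envelope could never be detected or traced, or that only the last envelope would be known. The document does not support that. It is silent on numbering, on keeping the list and on an opening record, and silence does not show their absence. A broken seal, or a count of used and unused envelopes against patients randomised, could reveal some exchanges. What can be said is that the protocol describes no means of detection or verification.

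**Conclusion.** The point holds as a minor one. As written, the assignment step does not ensure that the block sequence is followed, and the protocol describes no means of detecting an exchanged envelope or verifying the first assignment that intention to treat requires.

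The document does not show that allocation is biased, that concealment is absent, or that the intention-to-treat analysis cannot be done. The size of any effect cannot be computed, because the document gives no number of patients or envelopes and no exchange rate. Under the adverse assumptions above the false risk ratio is modest, and there is none if no exchange occurs. The case for a change rests on its low cost and on the fact that a lost assignment cannot be recovered later, not on demonstrated harm.

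**What to change.** Replace the assignment sentence in METHOD with:

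> Opaque sealed envelopes are numbered in the computer-generated order. After consent and eligibility are recorded, the patient identifier and date are written on the next envelope in sequence before it is opened. All used and unused envelopes are kept and reconciled to the generated list.

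Numbering restores the block order, the identifier preserves the first assignment, and reconciliation makes an exchange visible. If the present wording already meant the next envelope, the edit simply records that practice. Varied, undisclosed block sizes and a person outside the operating team to open the envelope would be useful additions but are not needed to settle this point.

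The cost is one sentence and slight administrative work by existing staff, with no extra patients.

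### The envelope naming the technique is chosen before surgery, so the surgeon probably knows the arm during a coracoclavicular step that appears common to both arms; opening it after that step would be a cheap improvement

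*Protocol*

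**What the plan says.** METHOD describes computer-generated allocation: "It will be randomized by block using a computer system". The allocations are printed and sealed in envelopes. On timing and use it says "Before the surgery one of the envelopes will be chosen, this envelope will contain one of the 2 techniques", continuing "from which the surgeon will use in the procedure".

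The arms are set out in the same section: "The coracoclavicular fixation with and without acromioclavicular stabilization will be compared making up two investigation groups". The general objective is to observe the clinical impact of the combined fixation and "compare it with the isolated coracoclavicular stabilization in the management of the unstable acromioclavicular luxation".

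SURGICAL TECHNIQUE describes a single operation, the one that ends in acromioclavicular fixation. The coracoclavicular part is completed first. After the Fiberwire is knotted over the plate, "then using fluoroscopy we visualize the adequate coracoclavicular reduction continuing to tie the Fibertape with a knot". The text then adds that it is "important not to cut the remaining suture so that it is set aside for the next step". The acromial incision and the tunnels for the acromioclavicular step follow, and at the end "both the remaining Fiberwire and Fibertape are tied using a surgical knot achieving AC fixation". There is no separate description of the isolated coracoclavicular operation.

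The only masking in METHOD is at follow-up, where patients are seen by a surgeon from another team who is unaware of the technique used.

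**The concern.** The research question is about what the acromioclavicular step adds. In a comparison of a base procedure with and without an added step, the difference can be credited to the addition only if the base procedure is carried out in the same way in both arms. A surgeon who knows beforehand that a second stabilizer will follow may tension the coracoclavicular sutures differently, or accept a different reduction, from one who knows that this fixation must hold alone. That is performance bias, and it could run in either direction.

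The outcomes exposed to it are central. PRIMARY OUTCOME lists implant failure and loss of reduction among the complications, and the specific objectives name coracoclavicular distance as the radiological parameter. All three depend on how well the coracoclavicular step was done. The masked follow-up surgeon protects the assessment of these outcomes but cannot undo a difference created in theatre.

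A surgeon cannot be masked to an added step that he or she performs. Here, however, the order of the operation would allow masking during the part that comes before it.

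**Working it through.** No arithmetic applies. The Protocol gives no figure on this point, and the question is when the allocation becomes known relative to the surgical steps. The check sets the relevant statements side by side.

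1. **When is the arm known?** METHOD has the envelope picked before surgery, containing the technique the surgeon is to use. It does not state the moment of opening. Because the envelope exists to tell the surgeon which operation to perform, and nothing delays that information, disclosure before the operation is the natural reading.

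2. **Is there a shared step?** METHOD defines the arms as coracoclavicular fixation with and without the acromioclavicular stabilization, and the general objective calls the comparator isolated coracoclavicular stabilization. Coracoclavicular fixation therefore belongs to both arms. That it is the *same* coracoclavicular fixation (same plate, tunnels and sutures) is an inference, because only the combined operation is described.

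3. **Does the shared step come first?** Yes, in the operation described. The order is: plate, subcoracoid sutures, Fiberwire knot over the plate, fluoroscopic check of the reduction, Fibertape knot, suture tails left uncut, then the acromioclavicular incision, tunnels and final knots.

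4. **Is there a usable branch point?** Yes, if step 2 holds. Once the coracoclavicular knots are tied, the reduction has been seen on fluoroscopy and the tails are still uncut, nothing specific to the acromioclavicular step has yet been done.

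5. **Does the shared step leave room for judgement?** Some. The implant, the drill size, the position of the first tunnel and the suture materials are specified. The reduction has only to be adequate, with no numerical criterion in that section, and suture tension is not specified.

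6. **Does anything else in the Protocol close the gap?** No. No statement postpones disclosure, and none says that the coracoclavicular step must be done identically whatever the arm. The masking at follow-up comes after the operation.

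Steps 1 to 6 support a risk of differential conduct in the shared step. They do not show that it will occur, or how large it would be.

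**The case against.** The strongest reply is that the Protocol states nothing wrongly here: allocation before surgery is a workable design, and opening the envelope during the operation is a refinement. Four parts of that reply stand.

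- **Chosen is not opened.** A reader might infer that the Protocol states the envelope is opened before surgery. It does not; that is only the likeliest reading. If later opening was intended, METHOD should say so.
- **The comparator is not described.** A reader might take it as settled that the coracoclavicular step is identical in both arms. It is not settled. ELECTION OF DESIGN speaks of two techniques in routine use, and the isolated one could use another construct. In that case there would be no common step after which to open the envelope. The proposal is therefore conditional on the sponsor's answer.
- **The technique is partly standardized.** If the described technique governs both arms, its fixed implant, drill and sutures narrow the room for differences, though they do not fix tension or what counts as an adequate reduction.
- **The randomized comparison remains valid.** A reader might conclude that the trial's main contrast is invalid. It is not. Intention-to-treat analysis is planned and validly compares the two strategies as delivered, including any effect of the surgeon's knowledge.

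Two further inferences lack support. One is that the planned per-protocol analysis would remove patients unevenly between arms: the Protocol gives no deviation rule and no evidence that events before the branch point would differ by arm. The other is a numerical size for the bias. The introduction cites a 21% loss of reduction from the literature, and one could assume a shift of 3 to 5 points in one arm and obtain relative risks of 18/21 = 0.86 to 16/21 = 0.76, or 24/21 = 1.14 to 26/21 = 1.24. These ratios only restate the assumption; nothing in the document supports that shift or any other.

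What the reply does not answer is attribution. The research question concerns the effect of adding acromioclavicular stabilization, and on the natural reading the surgeon performs the preceding, judgement-dependent step with the arm known.

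**Conclusion.** The point holds as a cheap improvement of minor to moderate severity. On the natural reading of METHOD, the surgeon knows the arm while doing a coracoclavicular step that appears common to both arms. That knowledge could affect tensioning and acceptance of the reduction, and through them loss of reduction, implant failure and coracoclavicular distance. The consequence is weaker attribution of any difference to the acromioclavicular step.

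The conclusion rests on two assumptions that the Protocol does not settle: that the envelope is opened when it is chosen, and that the described coracoclavicular step is used in the isolated arm too. Neither the size nor the direction of any bias can be derived from the document.

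**What to change.** First, the sponsor should confirm whether the coracoclavicular step in SURGICAL TECHNIQUE applies to both arms, and state this in the Protocol. The content of the control operation is for the sponsor to describe; this point does not propose one. If the constructs differ between arms, the Protocol should say so, and a difference in outcome could not then be credited to the acromioclavicular step alone.

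If the step does apply to both arms, change METHOD so that theatre staff other than the surgeon open the sealed envelope only after the coracoclavicular reduction has been confirmed on fluoroscopy and tied, with the remaining suture still uncut. The envelope then says whether the acromioclavicular step follows. The same edit should state whether a patient counts as randomized when the envelope is assigned or when it is opened, so that the intention-to-treat population is clear.

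The cost is a few sentences in METHOD, acromioclavicular instruments ready for every case, and handling of the envelope in theatre by someone other than the surgeon. The document does not show whether existing theatre staff can take this on. No additional patients or procedures are needed. The change protects only the shared step: the surgeon will necessarily know the arm from the branch point onwards.
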